5. TREATMENT PLAN

This is a multi-institution, CITN Cooperative trial of MK-3475 in patients with advanced MCC, who have not received prior systemic therapy for their disease. The trial is open-labeled and nonrandomized. Patients who have not received any previous systemic therapy for their disease will be treated with MK-3475, given every 3 weeks.

ORR, PFS, and DOR will be monitored by CT scans at week 13 and then at 9-week intervals. At 1 year, the scan frequency will be decreased to every 12 weeks. Responses and progression will be assessed by RECIST 1.1 criteria. OS will be chronicled and reported.

Patients who appear to progress on the initial scan, occurring at week 13 of therapy, will be allowed to continue on therapy if otherwise stable, until a confirmatory scan is obtained at 17 weeks. If the 17-week scan confirms progression, the study treatment will be discontinued and the patient will be followed for survival. Alternatively, MK-3475 treatment may be continued in the setting of progressive disease if the patient is otherwise clinically stable as defined by the following criteria:

- Absence of clinical symptoms or signs indicating clinically significant disease progression
- ECOG performance status ≤ 1
- Absence of rapid disease progression or threat to vital organs or critical anatomical sites (e.g., spinal cord compression) requiring urgent alternative medical intervention

Patients who appear to progress on any subsequent scan will be allowed to continue on therapy if otherwise stable, until a confirmatory scan is obtained 4 weeks later. If the scan repeated 4 weeks later confirms progression, the study treatment will be discontinued and the patient will be followed for survival, or alternatively, continue MK-3475 treatment, if patient is otherwise clinically stable as described above.

Therapy after progression is at the discretion of the patient and primary physician.

Patients with stable disease (SD) or partial response (PR) can be treated up to 2 years at patient and investigator discretion. Patients that achieve a complete response (CR) can discontinue treatment after 6 months of therapy provided that patient has had at least 2 cycles past validation of CR. Patients that recur off of therapy will be eligible for retreatment at patient and investigator discretion, provided they meet the criteria for retreatment and the trial is ongoing.

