5.1.1 CTEP IND Agent: MK-3475

Trial treatment should be administered on Day 1 of each cycle after all procedures/assessments have been completed as detailed on the Study Calendar ([Section 10](#)). Trial treatment may be administered up to 3 days before or after the scheduled Day 1 of each cycle due to administrative reasons.

MK-3475 treatment will be administered on an outpatient basis.

MK-3475 will be administered as a 30-minute IV infusion (treatment cycle intervals may be increased due to toxicity as described in Section 6.1). Sites should make every effort to target infusion timing to be as close to 30 minutes as possible. A window of -5

minutes and +10 minutes is permitted (i.e., infusion time is 30 minutes: –5 min/+10 min).

Study Treatment

Drug	Dose Potency	Dose Frequency	Route of Administration	Regimen/ Treatment Period
MK-3475	2 mg/kg	every 3 weeks	IV infusion	Day 1 of each cycle

Note: Calculate the required dose amount (2 mg/kg) based on subject's baseline weight. The dose amount should be recalculated if the subject's weight changes by more than 10% from the baseline weight measurement. If the patient's weight changes again by 10% or more (either increase or decrease) from the most recent weight used for dose calculation, recalculation of the dose is required.

Protocol [Section 8.1](#) provides specific instructions for MK-3475 dose preparation, and drug administration.

Treatment with MK-3475 study drug may continue until one of the following events occurs:

- Documented disease progression warranting alternative systemic therapy
- Intercurrent illness that prevents further administration of treatment
- Unacceptable adverse experiences (see [Section 6.1](#)).
- Need for >2 dose delays due to toxicity as per the dose modification guidelines described in Section 6
- Patient withdraws consent
- If in the opinion of the investigator and CITN Coordinating Center, a change or temporary or permanent discontinuation of therapy would be in the best interest of the patient.
- Pregnancy in patient
- Patient completes 24 months of treatment with MK-3475
- In patients with documented disease progression, treatment with MK-3475 can continue until one of the above occurs or until there is an increase in tumor burden of 25% or more following initial confirmation of progression.

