After a patient is discontinued from study therapy, an end of therapy visit should be performed as soon as possible following the decision to stop study drug treatment or in conjunction with last treatment visit if discontinuation of therapy is anticipated. A mandatory safety follow-up visit should be performed approximately 30 days after the last infusion of study medication. All AEs occurring within 30 days after the last dose of trial treatment will be recorded.

All patients who discontinue treatment due to progression will be followed for at least 30 days after their last dose of study drug or until initiation of a new anticancer treatment, whichever occurs first. After the safety follow-up visit, patients will be followed for survival via phone contact every 12 weeks.

Patients who discontinue study therapy without documented disease progression will have a mandatory safety follow-up visit approximately 30 days after the last infusion of study drug, and should continue to be monitored for disease status by radiologic imaging according to the guidelines described in the [Visit Requirements](#) and [Study Calendar](#) for post-treatment follow-up. Imaging may be performed at the investigative site or locally; scans will be collected and RECIST 1.1 assessments performed. Collection of disease assessments will continue until progression, start of a new anticancer therapy, death or end of study, whichever occurs first. Thereafter, patients who progressed or started new treatment will be followed for survival via phone contact every 12 weeks \pm 1 week.

AE reporting will begin with administration of first dose of study medication. All AEs occurring within 30 days after the last dose of study treatment will be reported. Serious adverse events (SAE) related and unrelated to trial treatment will be collected for 90 days after the last dose of trial treatment or the start of new anticancer treatment, whichever comes first. Afterwards, only SAEs that are related to trial treatment will be reported. All SAE should be reported to the Sponsor via CTEP Adverse Event Reporting System (CTEP AERS).

Patients who are discontinued from the study due to an unacceptable drug-related AE will be followed for resolution of the AE to Grade 0–1 or stabilization, and monitored for disease status by radiologic imaging until progression or initiation of a new therapy for their cancer, whichever occurs first.

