5.5 Duration of Follow Up

Upon discontinuation of therapy in patients without documented disease progression, every effort should be made to continue monitoring patients' disease status by radiologic imaging either at the investigative site or locally. Imaging will be collected and evaluated per RECIST 1.1.

- Year 1 Post-Treatment: Imaging will be performed Q 3 months (± 14 days) or as clinically indicated for the first year post-completion of treatment.
- Years 2 and 3 Post-Treatment: Imaging will be performed Q 6 months (± 1 month) or as clinically indicated during years 2 and 3 post-treatment.
- If the study remains open, imaging will be performed annually once patient has completed 3 years of follow up for disease assessment.
- Collection of standard of care disease assessments will continue until progression, start of a new anticancer therapy, death or end of study, whichever occurs first.

Patients removed from protocol therapy for unacceptable AE(s) will be followed for resolution or stabilization of the AE or 1 year, whichever is longer, in addition to following for disease assessments.

Disease assessments will be collected until (1) the start of new anticancer treatment, (2) documented disease progression, (3) death, or (4) the end of the study, whichever occurs first.

After progression or start of a new anticancer treatment, patients will be followed for survival ([Section 5.1.1](#)). Time to death will be chronicled for all patients.

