5.9 Discontinuation of Treatment Following Complete Response

Discontinuation of treatment may be considered for patients who have attained a confirmed complete response (CR) that have been treated for at least 24 weeks with MK-3475 and had at least two treatments with MK-3475 beyond the date when the initial CR was declared.

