10. STUDY CALENDAR

All baseline evaluations with the exception of scans are to be conducted within 14 days before start of protocol therapy. Scans must be done ≤4 weeks before the start of therapy. In the event that the patient’s condition is deteriorating, laboratory evaluations should be repeated within 48 hours before initiating the next cycle of therapy. **Treatment Year 1**

Trial Period	Screening Phase	Treatment Cycles Year 1 ^a				End of Tx	Post-treatment follow-up		
		To be repeated up to 2 years							
Tx Cycle/Title	Pre-Therapy	Cycle 1	Cycle 2	Cycles without scans (q 3 weeks)	Cycles with scans (Cycle 5 then q 9 weeks)(through Cycle 17) ⁿ	D/C therapy	Post-Tx Safety FU	Post-Tx Disease Assessments ^o	Survival Follow-up ^r
Scheduling Window (Days)	Day -28 to Day 0	Day 1 ±3	Day 1 ±3	Day 1±3	Day 1 ±3	At time of D/C	30 days ± 3 days post D/C	Variable frequency ^o post-D/C	Every 12 weeks ±1week phone contact
MK-3475 administration ^b		X	X	X	X				
Administrative procedures									
Informed Consent	X								
Concomitant Medications ^m	X		X	X	X	X	X		X
Medical History, demographics, etc.	X								
Clinical Procedures/Assessments ^a									
Review of AEs ^{d, e}		X	X	X	X	X	X	X ^e	
Physical Exam ^u	X	X	X ^u	X ^u	X	X	X		
Vital Signs, Height and Weight ^f	X ^f	X	X	X	X	X	X		
12-Lead EKG ^g	X	X				X			
Pulmonary function ^v	X								
ECOG PS	X	X	X	X	X	X	X		
Laboratory Assessments (Safety Labs)^{a,h,j,s}									
Pregnancy Test (Urine or Serum HCG) ^{h, i}	X					X			
CBC with Differential.	X		X	X	X	X	X ^l		
Comprehensive Serum Chemistry Panel ^j	X		X	X	X	X	X ^l		
Urinalysis ^{j, k}	X				X ^k		X ^l		
T3, FT4, and TSH ^{j, k}	X				X ^k		X ^l		

Trial Period	Screening Phase	Treatment Cycles Year 1 ^a				End of Tx	Post-treatment follow-up		
		To be repeated up to 2 years							
Tx Cycle/Title	Pre-Therapy	Cycle 1	Cycle 2	Cycles without scans (q 3 weeks)	Cycles with scans (Cycle 5 then q 9 weeks)(through Cycle 17) ⁿ	D/C therapy	Post-Tx Safety FU	Post-Tx Disease Assessments ^o ^t	Survival Follow-up ^r
Scheduling Window (Days)	Day -28 to Day 0	Day 1 ±3	Day 1 ±3	Day 1±3	Day 1 ±3	At time of D/C	30 days ± 3 days post D/C	Variable frequency ^o post-D/C	Every 12 weeks ±1week phone contact
Correlative Studies Blood Draws ^c									
Kyn/Trp ratio		X	X		X	X			
IFN-γ ELISpot/ICS		X	X		X	X			
Immunophenotyping		X	X		X	X			
T cell Gene Expression and Phenotyping		X	X		X	X			
MCPyV Antibody Levels		X	X		X	X			
Serum, plasma and PBMC storage		X	X		X	X			

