no evidence of disease progression will have scans every 3 cycles (every 9 weeks \pm 3 days) during the first year of treatment. Scan frequency will be decreased to every 12 weeks \pm 7 days during second year of treatment. For cycles with scans scheduled, scans should occur within 7 days before scheduled drug administration so that the investigator may evaluate the patient for possible progression before administering the next dose of study medication. The same imaging technique should be used in a patient throughout the trial with the exception that patients who have discontinued treatment without evidence of progression may have scans performed either at investigative site or locally. Local reading (investigator assessment with site radiology reading) will be used to determine eligibility and for patient management; Sponsor may collect radiological assessments for retrospective analysis by a central vendor. (See [Overall Trial Schema](#) and [Patient Visit Timeline](#)).

- o. In patients who discontinue study therapy without confirmed disease progression, a radiological evaluation should be performed at the time of treatment discontinuation (i.e., date of discontinuation \pm 4 week window). If a previous scan was obtained within 4 weeks before the date of discontinuation, then a scan at treatment discontinuation is not mandatory. Every effort should be made to continue monitoring their disease status by radiologic imaging at the investigative site or locally as follows: Year 1 Post-Treatment: imaging will be performed Q 3 months (\pm 14 days) or as clinically indicated. Years 2 and 3 Post-Treatment: imaging will be performed Q 6 months (\pm 1 month) or as clinically indicated. If the study remains open, imaging will be performed annually once patient has completed 3 years of follow-up for disease assessment. Collection of imaging for disease assessments will continue until (1) the start of new anticancer treatment, (2) documented disease progression, (3) death, or (4) the end of the study, whichever occurs first.
- p. A scan must be performed within 28 days before restarting treatment with MK-3475 after relapse from CR. Imaging should continue to be performed at frequencies described in footnote “n” above from the first dose of trial treatment or more frequently if clinically indicated. The Sponsor may collect radiological assessments for retrospective analysis by a central vendor.

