Note: Patients with confirmed progression will be declared as having progressive disease for statistical purposes even if they remain on study and respond continued MK-3575. Responses to continued MK-3575 will be chronicled and reported.

13.5.1.2 **PFS, DOR, and OS**

Survival curves for PFS, DOR, and OS will be estimated using the Kaplan-Meier

method.

For PFS, subjects without documented PD/death will be censored at the last disease assessment date. Any subject who is lost to follow-up will be included in the analysis and their PFS time will be censored on the last date that the subject was known to be progression-free, defined as the date of the last tumor assessment not indicating progression. As a sensitivity analysis, the primary analysis of PFS will be performed reconsidering subjects without documented PD or death who discontinued treatment or received new anticancer therapy to have been progressed at the date of treatment discontinuation or initiation of new anticancer therapy, whichever occurs later.

For OS, subjects without documented death at the time of analysis will be censored at the date last known to be alive.

For DOR, subjects who have not yet progressed by the last disease assessment will be censored at the last disease assessment—this is intended to describe censoring rules for the analysis where only responders are used.

Table 13.1 Analysis Strategy for Key Efficacy Variables

Endpoint/Variable (Description, Time point)	Statistical Method	Analysis Population	Missing Data Approach
Primary Hypothesis			
ORR	Simon Two Stage design analysis	Eligible subjects who receive at least 1 dose of treatment	See 13.5.1.
Secondary Objectives			
PFS	Estimation: Kaplan-Meier method for PFS curve estimation	Eligible subjects who receive at least 1 dose of treatment	Model based (censored at last assessment)
DOR	Summary statistics using Kaplan-Meier method	All responders	Nonresponders are excluded in analysis
OS	Summary statistics using Kaplan-Meier method	Eligible subjects who receive at least 1 dose of treatment	Model based (censored at last date)
Exploratory Objectives			

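### The PFS sensitivity analysis scores the permitted stop after confirmed complete response as progression, so a complete responder who never relapses fails earlier than one who relapses later

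*Combined protocol and SAP*

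**What the plan says.** The main PFS analysis in section 13.5.1.2 censors patients without progression or death at their last disease assessment. The sensitivity analysis in the same paragraph instead treats "subjects without documented PD or death who discontinued treatment or received new anticancer therapy to have been progressed at the date of treatment discontinuation" or at the start of new anticancer therapy, whichever date is later. The reason for stopping plays no part.

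The treatment plan allows one kind of stop because treatment has worked. Section 5 says: "Patients that achieve a complete response (CR) can discontinue treatment after 6 months of therapy", given at least two cycles after the CR is validated. Section 5.9 gives the same permission under a heading that itself uses the word discontinuation, with a minimum of 24 weeks of treatment and two treatments after CR was first declared.

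These patients are not lost to view. Section 5.1.1 says that patients who stop without documented progression "should continue to be monitored for disease status by radiologic imaging". Section 5.5 and footnote o of the study calendar (section 10) repeat this and set the schedule: every 3 months in the first year after treatment, every 6 months in years 2 and 3, and annually after that while the study is open.

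PFS at 16 months is to be compared with a historical 5% (sections 1.2 and 13.2.2).

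**The concern.** A sensitivity analysis of this kind asks whether PFS holds up if some patients who stopped without documented progression had in fact progressed. That makes sense when a stop may hide progression. A stop for confirmed CR is the opposite case: the patient stops because of success and is scanned afterwards. The rule replaces that observed progression-free follow-up with an event at the stop date.

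It also reverses the order of outcomes. Documented progression takes a patient out of the recoding and keeps its own date, so relapsing after the stop gives a longer PFS time than not relapsing. Taking the later of the two dates does not help, because a patient who needs no new therapy has only the stop date.

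The secondary hypothesis concerns durability at 16 months. A gap between main and sensitivity PFS could come from possible unrecorded progression or from permitted stops in durable responders, and the analysis as written would not separate them.

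**Working it through.** The plan states no figure for this analysis, so there is none to reproduce. The check has three steps.

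**1. Apply the rule to two patients.** Both have confirmed CR, stop at month 9 and start no new therapy.

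| Patient | Later course | Main PFS | Sensitivity PFS |
|---|---|---|---|
| A | Never relapses | Censored at last scan | Event at month 9 |
| B | Documented progression at month 20 | Event at month 20 | Event at month 20 |

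A has the better outcome and is scored as failing 11 months before B.

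**2. Can permitted stops fall before 16 months?** Inputs from sections 5, 5.9 and 10:
- Cycles last 3 weeks, so Day 1 of cycle c is 3(c − 1) weeks after the start.
- First-year scans are at cycles 5, 8, 11, 14 and 17, that is, 12, 21, 30, 39 and 48 weeks elapsed. Scans are then every 12 weeks: cycles 21 and 25, at 60 and 72 weeks.
- Months = weeks × 7 / 30.4375, so 16 months = 69.6 weeks.
- Assumption: a CR first seen at one scheduled scan is confirmed at the next.

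Sections 5 and 5.9 word the minimum differently, so both are shown. The 5.9 column is the latest of 24 weeks, two treatments after the first CR, and the confirming scan. The section 5 column is the later of 6 months and two cycles (6 weeks) after the confirming scan.

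| CR first seen (weeks) | Confirmed (weeks) | Earliest stop, 5.9 | Earliest stop, section 5 |
|---|---|---|---|
| 12 | 21 | 24 wk = month 5.5 | 27 wk = month 6.2 |
| 21 | 30 | 30 wk = month 6.9 | 36 wk = month 8.3 |
| 30 | 39 | 39 wk = month 9.0 | 45 wk = month 10.3 |
| 39 | 48 | 48 wk = month 11.0 | 54 wk = month 12.4 |
| 48 | 60 | 60 wk = month 13.8 | 66 wk = month 15.2 |
| 60 | 72 | 72 wk = month 16.6 | 78 wk = month 17.9 |

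A CR first seen at any of the five first-year scans permits a stop before month 16 under either wording. A CR first seen at the 60-week scan does not.

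**3. Effect on the 16-month estimate.** Take N = 50 (section 13.5), all followed past month 16. Kaplan-Meier at 16 months is then the proportion event-free. If k event-free patients stop for CR before month 16, the sensitivity estimate is (event-free − k)/50, a loss of k/50, or 2 points per patient. The values of k and the true 16-month PFS are assumptions; the documents give neither. Lower limits are exact (Clopper-Pearson), from the two-sided 95% interval.

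| k | Loss (points) | If true PFS is 20/50 = 40% | Lower limit | If true PFS is 15/50 = 30% | Lower limit |
|---|---|---|---|---|---|
| 1 | 2 | 19/50 = 38% | 24.7% | 14/50 = 28% | 16.2% |
| 3 | 6 | 17/50 = 34% | 21.2% | 12/50 = 24% | 13.1% |
| 5 | 10 | 15/50 = 30% | 17.9% | 10/50 = 20% | 10.0% |
| 7 | 14 | 13/50 = 26% | 14.6% | 8/50 = 16% | 7.2% |

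Every lower limit stays above 5%. With CR stops exempted and censored at the last assessment, the estimate returns to 40% or 30% for every k.

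**Beyond the landmark.** Section 5.1.1 lists "Patient completes 24 months of treatment with MK-3475" among the events that end treatment, whereas footnote t of the calendar separates patients who discontinue after CR from those who complete 2 years. If completion counts as discontinuation, every completer without progression becomes an event at month 24. This does not touch the 16-month figure, but it would pull down the later curve.

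**The case against.** The strongest reply is that this is a deliberate worst-case check. It is one sensitivity analysis of a secondary endpoint with no decision rule attached. It errs downward, and the main analysis beside it shows the observed follow-up. All of that is true and limits the weight of the point. But a pessimistic check should still not rank the best outcome below a worse one.

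A second reply is that post-treatment imaging also covers patients who stop for toxicity, so the argument from overwritten follow-up would exempt them too. The overwriting does occur there. What sets CR stops and planned completion apart is the reason: the patient stops because of success or because the planned course is finished. Keeping toxicity stops as events leaves the stress test intact.

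Third, all 50 patients are already enrolled in an open-label trial, and the change can only raise the sensitivity estimate. That stands as a reason to document the change openly. It is not a reason to keep a rule that gives the wrong ordering.

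Fourth, section 5.6 records the reason for removal from study by reference to section 5.4, which does not list a CR stop. Section 13.5.3 does plan to display the primary reason for discontinuation, and response status is collected in any case. Whether CR is a coded reason on the form should be confirmed.

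Finally, the CR stop is optional and its frequency is not given. The schedule shows that such stops can precede month 16, not that they did.

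**Conclusion.** The concern holds. As written, the sensitivity analysis makes an event of every CR patient who stops as permitted and stays progression-free without new therapy, and dates it earlier than the event of a similar patient who relapses later. The bias from these stops is downward: 2 percentage points of 16-month PFS for each such patient stopping before month 16, given 50 patients all followed past that point. Over an assumed 1 to 7 stops the loss is 2 to 14 points.

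The wording gap and the reversed ordering are certain. The size depends on a count that the documents do not give. Main PFS, its 16-month comparison with 5%, and response rate are unaffected. With assumed true PFS of 30% or 40%, the sensitivity estimate also stays above 5%. The plan should be corrected because the analysis understates robustness, but no main conclusion rests on it.

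**What to change.** Keep the sensitivity analysis for all other stops without documented progression or death, and for new anticancer therapy. Add to the sentence in section 13.5.1.2: *except that subjects who stop treatment for confirmed CR under section 5 or 5.9, or on completing 24 months of treatment, and who have not started new anticancer therapy, are not counted as progressed at the stop and are censored at the last disease assessment.* This also settles how 24-month completers are handled.

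Identify these patients from the recorded reason for discontinuation. If CR is not a coded reason, derive it from response and dosing dates. Sections 5 and 5.9 word the minimum time before a CR stop differently and should be reconciled, though the clause works under either.

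The cost is one clause and a small programming change. Because section 13 says there will be no separate SAP, the clause belongs in the protocol, with the date and reason recorded. Given the timing, report how many patients the exemption affects; showing the result under the current wording alongside would make the effect of the change visible.
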